12. PLANS FOR DISSEMINATING AND COMMUNICATING STUDY RESULTS

The rights of the investigator and of the sponsor with regard to publication of the results of this study are described in the investigator contract. As a general rule, no study results should be published prior to finalization of the Study Report.

1 INTRODUCTION

This document details the analysis and data representations that are planned to be presented as part of the Boehringer Ingelheim study 1245.149. This is a non-interventional study at approximately 25 sites in Saudi Arabia with prospective data collection to examine the risk of ketoacidosis, severe urinary tract infections, volume depletion, and dehydration associated with the new use of EMPAGLIFLOZIN compared to the new use of Dipeptidyl peptidase-4 (DPP-4) inhibitors in a total of 1,500 type-2 diabetes mellitus (T2DM) patients. The treating physicians will mainly be general practitioners (GP) and/or specialists including endocrinologists, diabetologists and internists.

Patients will be managed according to the local practice guidelines. The choice of treatment will be solely at the discretion of the participating physician. EMPAGLIFLOZIN and the comparator DPP-4 inhibitor will be administered according to the approved labels in Saudi Arabia.

2 OBJECTIVES AND END POINTS

This is a non-interventional study with new data collection.

2.1 Primary objective

The primary objective of this study is to estimate the incidence of

- Ketoacidosis
- Severe urinary tract infections (UTI)
- Volume depletion
- Dehydration

in T2DM patients initiating EMPAGLIFLOZIN compared with the incidence in T2DM patients initiating DPP-4 inhibitors.

The respective primary endpoints are incidences and occurrences of ketoacidosis, severe UTI, volume depletion and dehydration recorded as part of adverse event reporting and encoded according to MedDRA as defined in the Data Management Plan.

Statistical Analysis Plan (SAP)

Document Date: 17APR2019

Document Version: 1.0 Final

[figure not shown]
2.2 Secondary objectives

Further outcomes are estimates of the incidences of each primary outcome with respect to the Ramadan period (1st day of Ramadan to 29th day of Ramadan based on the Islamic Hijri calendar). Ramadan periods in 2019 and 2020 are given in Table 2-1 and visualized in Figure 2-1.

Table 2-1: Ramadan Time Periods 2019 and 2020

Ramadan Month 2019	May 5 th , 2019, to June 4 th , 2019, ± 1 to 2 days
Ramadan Month 2020	April 23 rd , 2020, to May 23 rd , 2020, ± 1 to 2 days

Figure 2-1: Study Time Flow including Ramadan Periods

The respective secondary endpoints are the same as the primary endpoints but restricted to incidences in the Ramadan periods. The follow-up period for each patient is one year.

3 STUDY OVERVIEW

The study will use an “incident users” design and compare new users of EMPAGLIFLOZIN with new users of DPP-4 inhibitors.

This study will be carried out by conducting successive surveys over the follow-up period. The investigator will be asked to record the information from the surveys in the case report forms

Statistical Analysis Plan (SAP)

Document Date: 17APR2019

Document Version: 1.0 Final

(e-CRFs) from each subject who was initially administered the drug following the study start date until the requested number of subjects is reached.

The index date for each identified new user is defined as the date on which they receive the index prescription for EMPAGLIFLOZIN or DPP-4 inhibitors.

Patients are enrolled if at least 18 years of age at the index date, diagnosed with T2DM in Saudi Arabia, and who have not used other SGLT2 inhibitors during the previous 12 months. Patients are not enrolled if they have known hypersensitivity to EMPAGLIFLOZIN, the comparator DPP-4 inhibitors or any of their excipients, if EMPAGLIFLOZIN or the comparator DPP-4 inhibitor is contraindicated according SFDA approved label, or if they are on prescribed fixed-dose combinations of SGLT2 inhibitors with DPP-4 inhibitors.

Follow-up will start the day after the index date and will continue until any of the following conditions are met:

- Death
- 12 months of follow-up
- specific exclusion criteria are met during follow-up
- the last continuous treatment of the index drug (EMPAGLIFLOZIN or DPP-4 inhibitor) plus a defined grace period (30 days after the end of the last prescription's days' supply in main analyses)
- a new treatment episode starts with any of the other index drugs.

Patients who discontinue an index drug and then subsequently initiate another index drug will not be allowed to re-enter the study.

Four study visits will be held, at baseline, after 16, 32 and 52 weeks of follow-up.

[figure not shown]
[REDACTED]

Statistical Analysis Plan (SAP)

Document Date: 17APR2019

Document Version: 1.0 Final

Figure 3-1: Study Visits

* from Visit 1

Table 3-1: Schedule of Visits

Assessment	Visit 1	Visit 2	Visit 3	Visit 4
Informed Consent	X			
Demographics	X			
Diagnosis	X			
Medical History	X			
HbA1c	X	*	*	*
Blood glucose level	*			
Other Laboratory/Renal Function	*			
Physical Examination (for vital signs)	X	*	*	*
Concomitant Medication incl. anti-hyperglycemic	X	#	#	#
Dose of Empagliflozin / DPP-4 inhibitor	X	#	#	#
Adverse Events		X	X	X
Study Completion Status		X	X	X

x = mandatory, * = if available, # = if changed

4 STATISTICAL METHODS

4.1 Scientific and Statistical Considerations of the Study Design

The incident-user design avoids comparing a population predominantly composed of first-time users of a newly marketed drug such as EMPAGLIFLOZIN with a population of prevalent users

Statistical Analysis Plan (SAP)

Document Date: 17APR2019

Document Version: 1.0 Final

of an older drug who may have stayed on the comparator treatment for a longer time and be less susceptible to the events of interest.

Propensity scores based on information prior to and including the index date will be used to account for potential confounding.

4.2 Sample Size Rationale

The sample size of 1,500 patients is based on SFDA requirements. The aim is to achieve comparable group sample sizes of 750 patients each. However given the real-world design of this study this may not be possible.

4.3 Randomization and Unblinding Procedures

This is a non-interventional observational study. Patients are not randomly allocated to treatment. Randomization and unblinding procedures are not applicable.

4.4 General Principles

All individual collected and derived data will be listed and described per group by means of summary tables presenting frequency counts and percentages for categorical data and arithmetic means, standard deviations, medians, minimum and maximum values for continuous data.

All statistical tests will be conducted with a two-sided significance level alpha of 0.05 and all analyses will be conducted using SAS statistical analysis software version 9.4 (SAS Institute, Inc., Cary, NC) or later.

Baseline (Visit 1) is defined as the last observation on or before the index date.

Let the *index period* define the time from index date to the end of treatment with either EMPAGLIFLOZIN or DPP-4 inhibitor, and the *follow-up period* the time from index date to the end of observation. The *index period during Ramadan* and the *follow-up period during Ramadan*, respectively, are the subperiods of index and follow-up periods, respectively, that will fall in the months of Ramadan as defined in Table 2-1 above, where June 6th 2019 and May 25th 2020 are assumed as the end of Ramadan for the two study years.

Statistical Analysis Plan (SAP)

Document Date: 17APR2019

Document Version: 1.0 Final

Durations of periods, time spans between visits and other times since the index date will be individually derived in days.

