9. RESEARCH METHODS

This is a non-interventional study with new data collection.

This study will cover the period between Q3 2018 and Q4 2020. The main goals of this study are to examine the risk of ketoacidosis, severe urinary tract infections, volume depletion, and dehydration associated with the use of Empagliflozin compared to the use of DPP-4 inhibitors in T2DM patients. The study will use an “incident users” design and compare new users of Empagliflozin with new users of DPP-4 inhibitors. The index date will be defined as the date on which each identified new user receives the index prescription for Empagliflozin or DPP-4 inhibitors. The definition of drug exposure for Empagliflozin will be any patient using at least one prescription of Empagliflozin tablets (10 or 25 mg) or fixed-dose combinations with metformin. The comparator group will be comprised of patients with at least one prescription of a DPP-4 inhibitor: sitagliptin, saxagliptin, linagliptin, vildagliptin, alogliptin (and fixed-dose combinations of these drugs with metformin). Each member of the population exposed to Empagliflozin must have at least one prescription for Empagliflozin, with or without other Glucose-lowering Drugs (GLDs,) and no prior prescriptions of a DPP-4 inhibitor or Empagliflozin during the available pre-index period. Each member of the population exposed to a DPP-4 inhibitor must have at least one prescription for a DPP-4 inhibitor, with or without other GLDs, and no prior prescriptions of a DPP-4 inhibitor or Empagliflozin during the available pre-index period.

Follow-up will start the day after the index date and will continue until any of the following conditions are met: date of death or after 12 months of follow-up, or the date during follow-up that specific exclusion criteria are met, the date of the last continuous treatment of the index drug (Empagliflozin or DPP-4 inhibitor) plus a defined grace period (30 days after the end of the last prescription’s days’ supply in main analyses), or the date in which a new treatment episode starts with any of the other index drugs. Patients who discontinue an index drug and then subsequently initiate another index drug will not be allowed to re-enter the study. Patients will be followed-up for 12 months.

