9.3.2 Exposures

The definition of drug exposure for Empagliflozin will be any patient using at least one prescription of Empagliflozin tablets (10 or 25 mg) or fixed-dose combinations with metformin. For the comparator group, the patients will have at least one prescription of DPP-4 inhibitors. DPP-4 inhibitor users included in this study will be using one of the following approved drugs in Saudi Arabia: Sitagliptin, Saxagliptin, Vildagliptin, Alogliptin, Linagliptin, or fixed-dose combinations of these drugs with metformin. [R17-3427]

Furthermore, each member of the population exposed to Empagliflozin must have at least one prescription for Empagliflozin, with or without other glucose-lowering drugs (GLDs), and have no prior prescriptions of a DPP-4 inhibitor or Empagliflozin during the available pre-index period. Each member of the population exposed to a DPP-4 inhibitor must have at least one prescription for a DPP-4 inhibitor, with or without other GLDs, and no prior prescriptions of a DPP-4 inhibitor or Empagliflozin during the available pre-index period.

Add-on therapy will be allowed after using the exposure of interest as the initial drug for new users. Therefore, using the drug as part of dual therapy or triple therapy will be allowed.

The use of studied medications will be defined on different levels: current use, recent use and discontinuation of the studied drugs. Current use of the index drugs will be defined from the date of prescription of Empagliflozin or DPP-4 inhibitor to the end of supply for that prescription plus a period of 30 days. Recent use will be defined from the end of current use (30 days after end of supply) until 90 days later (which is 120 days after end of supply).

Discontinuation of the index drug will be defined as no further prescription 120 or more days after the end of the last prescription's supply. Patients who discontinue an index drug and then subsequently initiate another index drug will not be allowed to re-enter the study.

Patients switching to or adding Empagliflozin to other antidiabetic medications will be compared to patients switching to or adding comparator treatment on the same background therapy. Identification of a "new-user" design is an appropriate method for studying second-line therapies in chronic conditions.

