9.7 DATA ANALYSIS

Details of all analyses and variables specification will be defined in a separate SEAP.

Patients are grouped according the exposure to either Empagliflozin or DPP-4 inhibitors. Data will be analysed per group. Let the index period define the time from index date to the end of treatment as defined in [section 9.3.2](#) by current use, and the follow-up period the time from index date to the end of observation as defined in [section 9](#). Incidences will be derived if events of interest occur in the respective period. The main analysis will consider index periods only, a secondary analysis will consider only the time of the index period in the month of Ramadan in every year, while sensitivity analyses will consider respective follow-up periods, overall or during Ramadan only. Times from index date to first occurrence will also be determined per event of interest and described by means of Kaplan-Meier estimates and median times with 95% confidence intervals, where appropriate.

All individual data will be listed and described per group by means of summary tables presenting frequency counts and percentages for categorical data and arithmetic means, standard deviations, medians, minimum and maximum values for continuous data. Baseline is defined as the last observation on or before the index date.

For the assessment of the primary and secondary objectives, the main data analysis will be conducted in two stages:

- 1) Construction of the PS by modelling the exposure to Empagliflozin vs. DPP-4 inhibitor;
- 2) Estimation of the effect of exposure to Empagliflozin on the risk of ketoacidosis, severe urinary tract infections, volume depletion and dehydration compared to those exposed to DPP-4 inhibitor.

Propensity score stratification will be the primary method to control for the confounders in the analysis phase. The stratification will divide the study population in several groups (max. 5 groups) based on their propensity score value. Propensity score matching will also be used as secondary method in the analysis phase.

All statistical tests will be conducted with a two-sided significance level alpha of 0.05 and all analyses will be conducted using SAS statistical analysis software version 9.4 (SAS Institute, Inc., Cary, NC) or later.

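### SAP 4.7.5 gives only index-period person-years for rates reported in four windows, and the plan ends the follow-up window in conflicting ways

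*SAP*

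**What the plan says.** **Windows.** SAP 4.9 analyses the four outcomes in the index period (primary), the index period during Ramadan (secondary), the follow-up period, and the follow-up period during Ramadan. Protocol 9.7 gives the last two their role: "while sensitivity analyses will consider respective follow-up periods, overall or during Ramadan only".

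**Index period.** SAP 4.4 lets it "define the time from index date to the end of treatment with either EMPAGLIFLOZIN or DPP-4 inhibitor" and mentions no grace period. Protocol 9.7 ends it by current use, which protocol 9.3.2 runs "to the end of supply for that prescription plus a period of 30 days".

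**Follow-up period.** SAP 4.4 makes it "the time from index date to the end of observation", and SAP 4.7.8 equates its length with the duration of observation. Protocol 9.7 refers to section 9 for that end. The section 9 stop list includes "the date of the last continuous treatment of the index drug (Empagliflozin or DPP-4 inhibitor) plus a defined grace period" and the start of another index drug. Protocol 9.2.2.5 and SAP 3 carry the same two stops; the SAP wording is "plus a defined grace period (30 days after the end of the last" supply. SAP 2.2, however, says each patient's follow-up is one year. Protocol 9 closes its stop-list paragraph by saying patients are followed for 12 months.

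**Person-time.** SAP 4.7.5 promises rates and rate ratios by group and period, then defines person-years as the summed lengths of index periods. Its time-to-event sentence, by contrast, censors at the end of the respective period. Figures 2.1 to 2.4 and Tables 15.18 to 15.21 (repeated for the other three outcomes) plan rates or rate ratios in all four windows.

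**Ramadan.** SAP 2.2 defines day 1 to day 29. SAP 4.4 uses the Table 2-1 periods, "where June 6th 2019 and May 25th 2020 are assumed as the end of Ramadan for the two study years".

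**The concern.** The person-years sentence fits protocol 9.7.2, which covers only the as-treated index-period analysis. In SAP 4.7.5 it governs a section that reports every window. Events counted in about a month of Ramadan would then be divided by most of a year of treatment time. The regulator asked for Ramadan data, and the stated objective is to estimate incidence, so the level of the rate matters as well as the ratio.

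The window conflict leaves the content of the follow-up tables open. On the stop-list reading they add little or nothing to the main analysis. On the one-year reading they add all off-drug and post-switch time. The same table titles could hold either analysis.

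**Working it through.** The documents give no figure to reproduce here, so the check compares the definitions and then works out person-time.

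**Step 1. One patient whose supply ends on day 90, with no switch.**
- Index period: 90 days (SAP 4.4 as worded) or 90 + 30 = 120 days (protocol current use).
- Follow-up period: 120 days (SAP 3, protocol 9 and 9.2.2.5) or 365 days (SAP 2.2).

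Under protocol 9.7 both windows are 120 days, so the sensitivity window coincides with the main one. The two readings of follow-up differ by 365 - 120 = 245 days.

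**Step 2. Inputs for the group calculation.**
- Stopping rates are not in the documents. Assumed: 10%, 25% or 40% stop by month 12, constant hazard, no direct switch, death or loss. lambda = -ln(1 - p)/365.
- Enrolment is assumed uniform from 1 July 2018 to 31 December 2019 (protocol milestones: Q3 2018 to Q4 2019).
- Ramadan is 5 May to 6 June 2019 and 23 April to 25 May 2020, 33 days each (SAP Table 2-1 starts, SAP 4.4 ends). The alternative is 29 days from the same starts (SAP 2.2).

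**Step 3. Mean days per patient.**
- A, index period without grace = (1 - exp(-365 lambda))/lambda
- B, with 30 days' grace = 30 + (1 - exp(-335 lambda))/lambda
- C, stop + 60 days = 60 + (1 - exp(-305 lambda))/lambda. This applies if the last dose falls 30 days before supply ends and the index period stops at the last dose.
- R33 and R29, mean Ramadan days inside the index period with grace, counted day by day over the enrolment dates

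| Assumed stopping | 10% | 25% | 40% |
|---|---|---|---|
| A | 346.4 | 317.2 | 285.8 |
| B | 349.3 | 324.4 | 297.4 |
| C | 352.0 | 331.1 | 308.3 |
| B/A | 1.008 | 1.023 | 1.041 |
| C/A | 1.016 | 1.044 | 1.079 |
| 365/B | 1.045 | 1.125 | 1.227 |
| 365/A | 1.054 | 1.151 | 1.277 |
| R33 | 32.1 | 29.5 | 26.8 |
| B/R33 | 10.9 | 11.0 | 11.1 |
| R29 | 28.2 | 26.0 | 23.6 |
| B/R29 | 12.4 | 12.5 | 12.6 |

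As a plain check with nobody stopping: 365/33 = 11.1 and 365/29 = 12.6.

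**Step 4. Error if index-period person-years are used in every window.** The factor is the index-period person-time divided by the window's own person-time, or the inverse where the window is longer.
- Ramadan rates in the index period: too low by 10.9 to 11.1 times (33 days) or 12.4 to 12.6 times (29 days).
- Follow-up rates on the one-year reading: too high by 4.5% to 22.7% (index period with grace) or 5.4% to 27.7% (without grace).
- Follow-up rates on the stop-list reading: no error under the protocol's definitions, 0.8% to 4.1% too high if the SAP index period ends at end of supply, and 1.6% to 7.9% in case C.

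**Step 5. Effect on the rate ratio when stopping differs by group.**
- Ramadan: 10.9/11.0 = 0.99 (25% on empagliflozin against 10% on DPP-4 inhibitor) and 10.9/11.1 = 0.98 (40% against 10%).
- One-year follow-up, 25% against 10%: 1.125/1.045 = 1.08.

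**The case against.** **The denominator.** A programmer would probably get this right. SAP 4.4 defines the Ramadan windows as subperiods and derives period durations for each patient, SAP 4.9.2 analyses the Ramadan endpoints like the primary ones, and the figures are titled by period. This stands to the extent that the eleven- to twelvefold error is a worst case, not a forecast. It does not change what 4.7.5 says: the only person-years rule there is the wrong one for three of the four windows.

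**The window.** Three detailed stop lists agree, and protocol 9.7 points to one of them. The 12 months in protocol 9 can be read as a maximum. Adverse-event collection to study end (protocol 11.2) and the table of patients stopping more than 120 days before study end (SAP 4.7.3) do not define an outcome window. This is fair, but SAP 2.2 says one year for each patient and nothing visible gives one passage precedence. If the stop list does prevail, the follow-up analysis essentially repeats the main one under the protocol's definitions.

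**Stronger readings.** A reader might infer that the Ramadan comparison between drugs is wrong by an order of magnitude. It is not, because the factor nearly cancels in the ratio. A reader might also infer that the study has no check on as-treated censoring. The documents do not support that: SAP 4.9.3 and part of SAP 4.10 are not visible, the protocol abstract plans further sensitivity analyses, and the intended purpose of the follow-up analysis cannot be judged from what can be read.

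**Conclusion.** The person-years rule in SAP 4.7.5 is wrong as written for every window except the index period. Applied literally, it would understate Ramadan rates by a factor of about 11 to 12.6. It would overstate one-year follow-up rates by 4.5% to 27.7%, depending on stopping and on whether the index period includes the grace days. These sizes rest on the assumed 10% to 40% stopping, constant hazard and uniform enrolment. The Ramadan factor hardly depends on the stopping rate; the follow-up error depends on it strongly. The primary index-period rates use the right denominator, and the Kaplan-Meier and Cox analyses do not use it.

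The end of the follow-up period is inconsistent across SAP 2.2, SAP 3, SAP 4.4 and protocol 9 and 9.2.2.5, and SAP 4.4 does not say whether the index period includes the 30 days. Both points should be settled before analysis. Neither shows that the primary comparison is invalid.

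**What to change.** **SAP 4.7.5.** For each rate and rate ratio, use the person-time at risk within the window being analysed: index, follow-up, or the Ramadan part of either. This is one sentence and needs no new data.

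**SAP 4.4.** State that the index period follows the protocol's current-use rule, including the 30 days. State one end-of-observation rule for the follow-up period, and reconcile SAP 2.2, SAP 3 and protocol 9 and 9.2.2.5 with it. Say also how the stop condition "specific exclusion criteria are met during follow-up" applies to each window.

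For the follow-up analysis to differ from the main one, its analysis window must extend past drug stop, for example to the earliest of 12 months, death, withdrawal or loss to follow-up. In that case report, by group, how many patients who stopped the drug were actually observed to week 52. This concerns analysis windows only, not how patients are treated.

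**Cost.** The SAP changes are wording, and the 52-week visit and adverse-event collection to study end are already planned. A protocol amendment would need ethics committee and authority approval (protocol 10.1). Off-drug and post-switch time dilutes the contrast, so the longer window should remain a sensitivity analysis. Recruitment was planned to start in Q3 2018, before the April 2019 SAP. If sites stopped observing patients after drug stop, rewording cannot recover that time.

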6. MILESTONES

Milestone	Planned Date
IRB/IEC approval	Q2 2018 – Q3 2018
Start of data collection (trial data) FPI	Q3 2018
Recruitment Period (LPI)	Q4 2019
Ramadan Month 2019	May 5th, 2019 – June 4th, 2019 ±1-2 days
Ramadan Month 2020	April 23 rd , 2020 – May 23 rd , 2020 ±1-2 days
Interim Progress Report to SFDA (as per the Saudi FDA templates)	Q4 2018, Q2 2019, Q4 2019, Q2 2020, Q4 2020
End of data collection (LPV)	Q4 2020
Final report of study results: CSR preparation	Q2 2021

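### The SAP's Ramadan analysis window is 33 days from the nominal start (31 to 35 over the stated tolerance), but the secondary objective defines a 29-day exposure

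*SAP*

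**What the plan says.** The exposure is defined in words and in dates, and the two do not agree.

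- **Objective.** SAP 2.2 defines the Ramadan period as "1st day of Ramadan to 29th day of Ramadan based on the Islamic Hijri calendar", and Protocol 8.2 does the same. That is 29 days.
- **Calendar dates.** SAP Table 2-1 gives "May 5 th , 2019, to June 4 th , 2019, ± 1 to 2 days" and "April 23 rd , 2020, to May 23 rd , 2020, ± 1 to 2 days". The milestones in Protocol 6 carry the same dates, for example "May 5th, 2019 – June 4th, 2019 ±1-2 days".
- **Analysis rule.** SAP 4.4 defines the index and follow-up periods during Ramadan as the parts of those periods "that will fall in the months of Ramadan as defined in Table 2-1 above", and then fixes the ends: "where June 6th 2019 and May 25th 2020 are assumed as the end of Ramadan for the two study years". It gives no matching rule for the start, and no rule for replacing the assumed dates once the true ones are known.
- **Use.** On the endpoints, SAP 2.2 says: "The respective secondary endpoints are the same as the primary endpoints but restricted to incidences in the Ramadan periods".

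Elsewhere the protocol speaks of the month without a day count. Section 9.3.3 evaluates the outcomes during the month of Ramadan, and section 9.7 restricts the secondary analysis to index-period time falling in that month each year.

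**The concern.** Ramadan is the only secondary objective, and the regulator asked for it. The rule in SAP 4.4 decides which events and which days count as Ramadan. It governs 12 of the 25 planned tables for each outcome (48 over the four outcomes), the Ramadan tables for adverse events and concomitant medication, and Figures 1.2, 1.4, 2.2 and 2.4.

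The assumed ends are the Table 2-1 end dates plus the full two-day tolerance, and the text shows no corresponding shift of the start. A window built this way is longer than the exposure in the objective. Because the start keeps its tolerance while the end does not, two programmers could also build different windows from the same text.

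**Working it through.** **Inputs.** Defined exposure: 29 days (Protocol 8.2, SAP 2.2). Nominal starts: 5 May 2019 and 23 April 2020, each with a tolerance of up to 2 days (Table 2-1). Table ends: 4 June 2019 and 23 May 2020. Ends fixed for analysis: 6 June 2019 and 25 May 2020 (SAP 4.4).

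**Step 1: lengths, counting both end days (end minus start plus 1).**

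| | 2019 | 2020 |
|---|---|---|
| Table 2-1, nominal | 5 May to 4 June = 31 | 23 April to 23 May = 31 |
| SAP 4.4 end, nominal start | 5 May to 6 June = 33 | 23 April to 25 May = 33 |
| Day 1 to 29 from nominal start | ends 2 June | ends 21 May |

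The 29 days cannot be reproduced from the dates. Leaving out one end day gives 30 for the table and 32 for SAP 4.4. Of the four surplus days, two come from Table 2-1 and two from the assumed ends.

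**Step 2: start tolerance, with the SAP 4.4 end held fixed.** The results are the same in both years.

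| Start shift (days) | Length | Excess over 29 | Share of window |
|---|---|---|---|
| −2 | 35 | 6 | 6/35 = 17.1% |
| −1 | 34 | 5 | 5/34 = 14.7% |
| 0 | 33 | 4 | 4/33 = 12.1% |
| +1 | 32 | 3 | 3/32 = 9.4% |
| +2 | 31 | 2 | 2/31 = 6.5% |

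**Step 3: if a 30-day month is meant (assumption).** At the nominal start the excess is 33 − 30 = 3 days, or 3/33 = 9.1% of the window.

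**Step 4: person-time.** At the nominal start, 33/29 = 1.138, so person-time is 13.8% above the definition. For 750 patients exposed throughout one Ramadan (assumption), 750 × 33/365.25 = 67.8 person-years against 750 × 29/365.25 = 59.5.

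**Step 5: effect on a Ramadan rate.** Let the rate on defined Ramadan days be R times the rate on the surplus days. The window then shows (29R + 4)/33 times the surplus-day rate. If R = 1 there is no distortion. For an assumed R of 2, the result is (58 + 4)/33 = 1.88, so the Ramadan rate is understated by about 6% (1.88/2 = 0.94). For windows of 31 and 35 days the figures are 1.94 and 1.83. R is assumed here because the documents give no rate inside or outside Ramadan.

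**Step 6: effect on the between-group ratio.** Suppose the ratio of empagliflozin to DPP-4 inhibitor is θ on Ramadan days and also θ on the surplus days, and the surplus days form the same share of person-time in both groups. The pooled ratio is then θ whatever R is. It moves only if the ratio on the surplus days differs.

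**The case against.** The best defence is timing. The SAP is dated 17 April 2019, before the nominal start of either Ramadan. Taking the upper tolerance as the end keeps late Ramadan days from being lost, and the text openly calls the dates assumed. That explains the choice when it was made. It does not explain keeping it: data collection runs to Q4 2020 and the report is planned for Q2 2021 (Protocol 6), so both years' dates will be known before analysis.

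A second defence is that 29 days is not the only wording. Protocol 9.3.3 and 9.7 refer to the month, and SAP 4.4 itself refers to months. This stands, and it means the definition has to be reconciled, not simply set to 29. It does not rescue the window, which exceeds even a 30-day month by 3 days at the nominal start.

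Three stronger readings are tempting, and the documents do not support them.

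- *That at least four days are surplus and all fall after Ramadan.* Four days depends on the nominal start. If Ramadan in fact began two days late (7 May 2019) and the nominal start were used, day 29 would be 4 June, with two surplus days before and two after.
- *That a planned rate ratio of 2.0 would come out as 1.88.* That figure compares Ramadan with non-Ramadan rates under an assumed R. The readable SAP plans no such comparison. Tests compare the two drug groups (SAP 4.6), ratios are empagliflozin to DPP-4 inhibitor (SAP 4.7.5), and the Ramadan endpoints follow the primary methods (SAP 4.9.2).
- *That the data are so sparse that a single misassigned event decides the result.* Protocol 9.9 concedes that numbers may be low for ketoacidosis, but neither document gives an incidence rate from which to derive an expected count.

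**Conclusion.** The inconsistency is real and should be corrected. It lies inside the SAP (2.2 against Table 2-1 and 4.4), and Protocol 8.2 and 6 show the same split between 29 days and 31. Followed as written, SAP 4.4 gives a window 4 days too long against the 29-day definition at the nominal start, with a range of 2 to 6 days over the tolerance.

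The consequence is limited. The descriptive Ramadan incidence rates are diluted if risk differs in Ramadan, and by a modest amount under the rate assumed in the working. The comparison between groups is affected only if its ratio differs on the surplus days. The primary index-period analysis does not use the window. The person-year figures rest on 750 fully exposed patients per group, which the documents do not guarantee: SAP 4.2 says equal groups of that size may not be reached, and Protocol 9.9 expects some patients to leave before Ramadan.

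**What to change.** In SAP 4.4 and Table 2-1, replace the assumed and approximate dates with the officially announced first day of Ramadan in Saudi Arabia for 2019 and for 2020, running through day 29 as in the objective. If the whole month is intended, as Protocol 9.3.3 and 9.7 suggest, run the window through the announced last day and amend the objective in Protocol 8.2 and SAP 2.2 to match. Either way, state one definition, drop the tolerance, and use the same dates for events and person-time in every Ramadan output.

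The cost is a start and an end date per year in the SAP and the analysis program, plus a wording change to the objective if the whole month is chosen. No new data are needed.
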